3.3. Reporting serious or unexpected device-related adverse events

A serious adverse event is any untoward occurrence that:

- Results in death
- Is life-threatening; (a non life-threatening event which, had it been more severe, might have become life-threatening, is not necessarily considered a serious adverse event)
- Requires inpatient hospitalization or prolongation of existing hospitalization
- Results in significant disability/incapacity
- Is a congenital anomaly/birth defect

3.4. Unanticipated adverse device event

An unanticipated adverse device event is defined as an adverse event caused by, or associated with, a device, if that effect or problem was not previously identified in nature, severity, or degree of incidence.

Serious or unexpected adverse events must be reported to the coordinating center immediately via completion of the online serious adverse event form.

The principal investigator will notify all participating investigators of any adverse device event that is both serious and unexpected. Notification will be made within 10 days after the PI becomes aware of the event.

The PI is responsible for informing their IRB of serious study-related adverse events and abiding by any other reporting requirements specific to their IRB.

3.5. Potential risks and side effects

Loss of confidentiality is a potential risk and is protected by the safeguards discussed above. Hypoglycemia, hyperglycemia, and ketone formation are always a risk in subjects with type 1 diabetes. Subjects will be closely monitored for this. When wearing CGM sensors there are risks of skin rashes, allergic reactions to tape, infections at the insertion site, or small pieces of the sensor breaking off or remaining under the skin. These risks will be monitored, but study staff will not oversee insertions, tracking of sensor information, and other diabetes device information.

3.5.1. Hypoglycemia

There is always a risk of hypoglycemia for patients with insulin-dependent diabetes. The frequency of hypoglycemia during this study is not expected to be greater than the risk incurred during daily living. If severe hypoglycemia occurs, it is readily treated with either oral glucose or glucagon injection. To minimize the risk of hypoglycemia due to "stacking" insulin doses, study participants will be instructed in their initial education not to take rapid acting insulin injections to correct hyperglycemia more than once every 3 hours. The low alert level

will be set at 75 mg/dL for all study participants at the outset of the study; however, participants can change these alerts if they would like.

3.5.2. Hyperglycemia

Hyperglycemia and ketonemia can occur if insulin delivery is attenuated or suspended for an extended period. This is a risk of type 1 diabetes that is not expected to be greater during the study period than it is during daily living. If severe hyperglycemia occurs, participants will be advised to treat with insulin therapy or to seek medical attention from their diabetes care team.

3.5.3. Lancing risks

Finger lancing is part of the usual care for people with diabetes and should not be a significant contributor to risks in this study. A small drop of blood will be obtained by finger stick to measure blood glucose and HbA1c. This is a standard method to obtain blood for routine hospital laboratory tests. Pain is common at the time of lancing. In about 1 in 10 cases, a small amount of bleeding under the skin will produce a bruise. A small scar may persist for several weeks. The risk of local infection is less than 1 in 1000.

3.5.4. Sensor site risks

There is a possibility of CGM sensor site risk. Whenever the skin is broken there is the possibility of an infection. CGM sensors are inserted under the skin. There may be bleeding where the sensor is inserted, which can cause bruising. CGM site infections occur very infrequently, but, if an infection was to occur, oral and/or topical antibiotics can be used. The risk of skin problems could be greater if a sensor is left in longer than recommended. On rare occasions, the sensor wire may break or detach from the sensor pod. There is a remote chance that sensor fragments could remain under the skin if the sensor breaks during normal wear. Subjects may also develop skin irritation or allergic reactions to the adhesives used to secure the CGM. If these reactions occur, different adhesives (such as with IV 3000, Tegaderm, etc.) will be tried, sites will be rotated frequently, and a mild topical steroid cream or other medication may be required. All participants will be carefully instructed about proper use of sensors.

3.5.5. Other potential risks

A potential source of risk in this study is the risk of gathering sensitive social, behavioral, and medical information. Data collection via the internet will be conducted through secure applications (REDCap). There are no known psychological risks to subjects completing self-report attitude and behavior rating scales, or participating in intervention sessions. However, the survey and intervention topics may contain items or questions that make the subjects feel uncomfortable in that they ask about their physical and psychological health and feelings/emotions. Subjects will be informed that any items on questionnaires or topics discussed in the intervention modules that produce these effects may be skipped or ignored. Subjects will also have the option of not participating in conversations or exercises in the interventions that cause them discomfort. They will also be free to withdraw at any time. All intervention modules will be carried out by a highly trained, doctorate level psychologist. There are no known risks to audio recording intervention sessions. All audio recorded information will remain confidential and will only be accessed by study team members. Use of BG meter downloads offers no increased risk over standard care. Data downloaded from CGM and the home glucose meter will be collected for the study as measures of diabetes self-management behaviors. Some people may be uncomfortable with the researchers' having such detailed information about their daily diabetes habits. The respondent burden for completion of all data collection at each assessment point is approximately 30-45 minutes total. All participants will be clearly informed of the time required for participation, the study duration, and the nature of the data to be collected. It is not anticipated that any of the data collection instruments will cause any adverse effects.

3.6. Adequacy of protection against risks

3.6.1 Informed Consent and Assent.

Interested participants may contact members of the study team directly or may be asked during a clinic visit if they wish to learn more about the study and be approached by a member of the study team. Either by phone or in person, a member of the study team will conduct screening for eligibility and enter this information into the secure server (REDCap). Eligible adults who are interested in participating will be provided with an informed consent form and HIPAA waiver, either electronically or hard copy. The study team member will then explain the purposes, benefits and risks of the project and offer them an opportunity to ask questions and/or decline participation. If still interested in participating, a full description of the nature of the study, the requirements of their participation in it, and the risks and benefits of the study will be explained to potential participants by the principal investigator or a trained research assistant. If an individual declines participation, the reasons for this will be documented and permission to record relevant demographic data from clinic records will be requested. This procedure allows for comparisons to be made between those who do and do not participate. If they consent to participate, they may do so either in written form or electronically.

All minorities will be encouraged to participate. Economically and educationally disadvantaged people, and participants who are employed at the clinical center (Stanford) will be eligible to enroll in this study if they meet all the study criteria. Subjects will be recruited from our clinics, through T1D community organizations, and through IRB approved patient recruitment lists. We will also use IRB approved recruitment materials to post the study on clinicaltrials.gov and to Stanford's research and department websites. Participants may self-select to join the research by responding to advertisements on social media. These posts will provide contact information for the research staff at each site. We will not interact with potential participants or enrolled participants through these media. We will actively work to prevent harm to all subjects enrolled in the study. We will work to avoid coercion by allowing equal enrollment opportunities for employees, as well as non-university affiliated subjects. We will ensure that all participants are informed that their participation is voluntary, that they will receive no ill treatment should they decide to not participate, and that they will receive no special advantages, aside from those mentioned in the "benefits" section of the consent, for participating in the study.

Participation will be voluntary. All participants must provide consent prior to inclusion in this research study. The primary investigator or a trained research coordinator will explain the nature, purpose, expected duration, and risks of study participation to each eligible participant. The primary investigator or trained research coordinator will also obtain consent and authorization for the release of personal information.

3.6.2. Protections Against Risk

All protocols and consent documents will be approved by Stanford's IRB. All members of the research team have and will maintain current training in the ethical conduct of research. [name] has completed rigorous training in the protection of human subjects, including CITI training, and graduate coursework at Yeshiva University. Research assistants and mentors/advisors working on the project will also complete standardized training in the protection of human subjects. The plan for protecting privacy and confidentiality recognizes that the protection of privacy in studies involving sensitive data is of utmost importance. We will attempt to do this in several ways. The PI or a trained RA will introduce the study to eligible participants and explain the purposes, benefits, and risks of the project to the subjects, and offer them an opportunity to ask questions and/or decline participation. The voluntary and confidential nature of the research, as well as limits to confidentiality, will be highlighted during informed consent process. Study participation will not interfere with clinical care and all patients have standard access to their treatment team on a routine (clinical care) and emergency basis. All responses to interview items will be given by subjects in private. Internet data collection will only occur through tools and resources that have acceptable security features. We will minimize all communications that involve names or other identifying information. All clinically relevant and study information will be kept in locked files in locked offices or password protected files.

Audio recordings of intervention sessions will be for quality control purposes only to ensure that sessions are delivered in a consistent way across participants. These audio recordings will be saved on a password-

protected secure server, will be reviewed by the PI, and will be deleted upon review. Information about subjects will not be accessible to any nonauthorized study personnel without the written consent of the subject. In all datasets we will use ID numbers only. A separate dataset linking names with ID numbers will be accessible only to authorized study personnel under the direction of the PI.

There will be an endocrinologist on call 24/7 for any severe events that should occur. Likewise, a licensed clinical psychologist is available for any concerns on the psychological side. Severe events are not anticipated but will be monitored. Study personnel are always available for questions. Hyperglycemia and ketone formation are always a risk in subjects with type 1 diabetes and subjects will be closely monitored for this. Subjects will have blood ketone meters provided through routine clinical care. Insulin can be given as a subcutaneous injection to treat hyperglycemia. Participants will be encouraged to contact their diabetes clinical care team and will also have access to phone numbers for a study physician. Participants in both groups will receive instruction about inserting and calibrating the sensor and will receive standardized introductory education about CGM. Participants are free to check blood glucose via fingerstick at any time and encouraged to do so if/when they notice a potential discrepancy between CGM and fingerstick values. A person trained in delivering education about CGM will deliver the education about CGM use and will assist with inserting the first sensor. This individual will be available to assist with questions from participants. In addition, Dexcom representatives are available to the participants for technical questions or issues with the system, just like the access any Dexcom user has.

3.7. Study stopping criteria

Individual subjects will be removed from the study for the following reasons: pregnancy, study-related adverse events (i.e. severe hypoglycemia, loss of consciousness, hypoglycemia related seizure, DKA related to study-related event requiring hospitalization), severe skin infection requiring systemic antibiotics, severe reaction to sensor tape, or other reasons that develop during the study that in the judgment of the investigator make it unadvisable for the subject to continue with the study

CHAPTER 4: MISCELLANEOUS CONSIDERATIONS

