2.7. Data analysis plan

Our team has extensive experience in the use of web-based assessment, data management and data analysis. Quantitative data will be entered into an online encrypted, HIPAA-compliant data management system, REDCap, with secure access for unique study IDs assigned to each participant. REDCap survey data is then ready for download by study staff and will be imported into SPSS for data cleaning and analysis. CGM data will be downloaded via Dexcom Clarity and LibreView which create a CSV file for transfer to REDCap and data analysis programs.

Demographic, medical, psychosocial variables, and some outcome measures are surveys and multi-item scales that participants will answer in REDCap. Psychometric properties of scales will be assessed before proceeding to investigate the proposed aims. These psychometric properties include item-total correlations and Cronbach's α to assess reliability. Total scores and subscale scores, when available, will be calculated and used for statistical analyses. Descriptive statistics will calculate frequencies, means and standard deviations for study variables. Independent samples t-tests and χ^2 analyses will assess potential differences between groups at baseline in demographic, psychosocial and diabetes variables. Analyses for Hypotheses 1&2 will follow the intention-to-treat principle.

To test Hypotheses 1&2, we will first conduct a treatment group comparison (ONBOARD vs. CGM-only) of the change in A1c, the primary outcome, from baseline to 3, 6, and 12 months. Specifically, we will use linear mixed models to model changes in A1c as a function of time, intervention assignment, and group-by-time interaction. These models will include a subject-specific random effect to account for the correlation of

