outcomes over time within a subject. We will examine change from baseline for each outcome as the dependent variable. We will begin by fitting models with minimum covariates prior to considering additional covariates. Similar models will be used to examine secondary outcomes of time in range, days of CGM wear (Hypothesis 1), diabetes distress, and perceived CGM benefit (Hypothesis 2). We will reference information criteria (e.g., Akaike's) to inform model selection decisions. Beyond testing the groups-by-time interaction term, custom contrasts will assess group differences at each time point. Exploratory analyses will examine differences between subgroups over time after primary, intent-to-treat analyses are completed. Additional exploratory analyses will examine patient-level predictors of CGM wear (e.g. age, gender, diabetes duration). For the CGM-continuer subgroup, we will conduct exploratory longitudinal analyses using CGM data to look at changes in time in range. We will adjust for multiple comparisons by using the Benjamini-Hochberg procedure and a false discovery rate of 0.05 (78). Analyses will initially be conducted without imputation for missing values, using the missing-at-random approach (79) and then multiple imputation will be used to supply values for missing data. We will conduct sensitivity analysis by multiple imputation to compare the effects.

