Enrolling and randomizing a sample of 178 adults with T1D (1:1 randomization; 89 per arm) will be sufficient to investigate the hypotheses in this study. Based on our previous related work, we estimate 15% attrition, yielding a final sample size of 76 participants per arm (152 total). This target sample size is based on the following pieces of data. First, effect sizes comparing CGM to non-use in adults with T1D are in the moderate ($d=.40\text{--}.50$) range (8, 75, 76), showing improvements in A1c and time in range during CGM use. Further, standardized effects of diabetes behavioral interventions for adults are in the small to moderate range with .35 to .40 SD unit differences (43, 77). In the proposed study, we hypothesize group differences in A1c of a similar or greater magnitude will be driven by a combination of greater sustained use of CGM over the 12-month follow-up period in the ONBOARD program and added utility and benefits from use resulting from the ONBOARD program. Sample size estimates for comparison of ONBOARD and CGM-only are based on intent-to-treat analyses, $\alpha=.05$, 80% power, autocorrelation of .50 (7), a repeated measures ANOVA on change between the 2 groups from baseline to 3, 6 and 12 months. A sample of 89 participants assigned to ONBOARD and 89 to CGM-only will provide power to exceed 0.80 for the primary outcome of A1c for moderate effects of $d=.35$ or greater. The sample size allows detectable mean differences in the magnitude of $A1c \geq 0.5\%$ (conservatively assuming 1.2 SD; recent registry data suggests our SD will be closer to 1.0). A 0.5% A1c is the minimum clinically significant difference regarded by physicians and stakeholders. Treatment guidelines and algorithms from ADA/EASD and UK National Institute for Clinical Excellence have recommended evaluating new treatment regimens by whether A1c is lowered by 0.5% or more. Between clinic and wider T1D community, we will have ample ability to reach our recruitment goal.

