4.4. Subject withdrawal

Participation in the study is voluntary and a subject may withdraw at any time. The investigator may withdraw a subject who is not complying with the protocol. For subjects who withdraw, their data will be used up until the time of withdrawal.

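### Sections 3.7 and 4.4 take participants out of the study without providing for further A1c or survey collection, so obtainable outcomes are lost to the intention-to-treat comparison for reasons that may relate to those outcomes

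*Combined protocol and SAP*

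**What the plan says.** Section 3.7 acts at the level of the study: "Individual subjects will be removed from the study for the following reasons: pregnancy, study-related adverse events". The adverse events named include severe hypoglycemia, loss of consciousness, seizure and DKA. Skin reactions and an investigator-judgment clause follow. The section does not distinguish stopping the device or the sessions from stopping assessment.

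Section 4.4 adds a discretionary route, "The investigator may withdraw a subject who is not complying with the protocol", and a data rule, "For subjects who withdraw, their data will be used up until the time of withdrawal". Section 2.3 makes active CGM use for the first 12 weeks a requirement in both arms.

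Section 2.7 states that "Analyses for Hypotheses 1&2 will follow the intention-to-treat principle" and that "Sample size estimates for comparison of ONBOARD and CGM-only are based on intent-to-treat analyses". For the mixed models it says "We will examine change from baseline for each outcome as the dependent variable". Missing values are handled first under missing at random, then by multiple imputation as a sensitivity analysis.

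On adverse events, section 3.2 (Recording of adverse events) has the investigator ask about them at visits and phone calls, and follows events still continuing after discontinuation. Section 2.5 gives four post-baseline visits to ONBOARD only; later assessments in both arms are by mail or online.

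**The concern.** An intention-to-treat comparison needs outcomes from everyone randomized, whatever happens to their treatment. Here the A1c kits and surveys are already remote and do not depend on wearing a sensor or attending sessions, so they could usually still be obtained after someone stops either. As written, nothing says they will be.

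The reasons for leaving are not neutral. Severe hypoglycemia and DKA are plausibly related to A1c. Withdrawal for non-compliance may matter more: stopping CGM early breaches the 12-week requirement, sustained CGM use is part of the mechanism that section 2.7 gives for the expected A1c difference, and days of wear is a secondary outcome. Withdrawing early stoppers would select on what the intervention is meant to change. Values not collected cannot be recovered later.

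A smaller issue is that adverse events are sought at contacts that are scheduled unequally between arms in the first 12 weeks. Several 3.7 grounds are events that must first come to light, so unequal elicitation could in principle lead to unequal removal.

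**Working it through.** **1. The plan's own figure.** 89 per arm with 15% attrition: 89 × 0.85 = 75.65, or 76 per arm, as section 2.7 states. The plan therefore allows for 89 − 76 = 13 losses per arm. It does not say how many would be removals under 3.7 or 4.4.

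**2. What is provided after removal.**

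| Item | Provision after removal or withdrawal |
|---|---|
| Continuing adverse events | Followed to outcome (3.2, Recording) |
| Data already collected | Used up to withdrawal (4.4) |
| A1c kits at 3, 6, 12 months | None stated |
| Surveys at 3, 6, 12 months | None stated |

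**3. Data lost.** Planned post-baseline A1c values per arm: 89 × 3 = 267. A person removed before month 3 loses all three, and so contributes no observed change from baseline. One to three such people lose 3 to 9 values: 3/267 = 1.1% to 9/267 = 3.4%. The same count applies to surveys.

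**4. Possible bias in the A1c difference.** Neither the number of removals nor the outcome gap is in the documents; both are assumed. Let k be the excess removals in one arm before month 3, and let the gap be the difference in mean A1c change between removed and retained people, taken as equal in both arms. An analysis of observed values is then off by

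bias = (k / 89) × gap.

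| k | gap 0.5 | gap 1.0 | gap 1.5 | share of the 0.5-point target |
|---|---|---|---|---|
| 1 | 0.0056 | 0.0112 | 0.0169 | 1.1% to 3.4% |
| 3 | 0.0169 | 0.0337 | 0.0506 | 3.4% to 10.1% |

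Entries are A1c percentage points. The formula is linear, so each further excess removal adds 0.006 to 0.017.

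**5. Against sampling error.** Section 2.7 gives the SD as "conservatively assuming 1.2 SD; recent registry data suggests our SD will be closer to 1.0". At its correlation of 0.50, the SD of a change score is SD × √(2 × (1 − 0.5)) = SD. With 76 per arm at one time point, SE = SD × √(2/76), which is 0.195 at SD 1.2 and 0.162 at SD 1.0. The bias is then 0.03 to 0.10 SE for k = 1 and 0.09 to 0.31 SE for k = 3.

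**6. Scheduled contacts.** Post-baseline visits: 4 in ONBOARD (the intervention sessions, the first 2 weeks after CGM initiation) and 0 in CGM-only. No phone calls are scheduled in either arm. Remote assessments: 3 in each arm. The effect on event counts cannot be derived.

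**The case against.** The strongest reply is that the plan already deals with incomplete participants: 15% attrition is budgeted, missing-at-random models are specified, and multiple imputation follows. That stands. A reader might infer that 3.7 and 4.4 flatly contradict the intention-to-treat statement. The documents do not support that, because intention-to-treat with planned missing-data handling is coherent. What remains is narrower: these methods suit values that could not be obtained, they rest on an assumption that outcome-related removal strains, and the plan is silent on collecting values that could be obtained.

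Second, the data rule in 4.4 is written for people who withdraw and is not explicitly extended to 3.7 removals. The consent form is not among the documents and might provide for continued collection. Both points stand as limits.

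Third, the numbers are small and assumed, section 3.6.2 does not anticipate severe events, and bias of the kind calculated needs unequal removal, which is possible but not shown. A reader might also want a ceiling on type I error. None follows. The largest case above (0.0506, SD 1.0) gives 6.1% with the single-time SE. With the mean of three follow-ups at correlation 0.50, SE = 0.162 × √(2/3) = 0.132, and the same case gives 6.7%. Both describe one corner of an assumed grid.

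Fourth, on adverse events, a reader might infer that CGM-only has no scheduled medical reporting, or that the ONBOARD visits exist for safety. Neither is so. The four visits are intervention sessions, and extra contact is inherent in the comparison. Table 4 schedules a demographic/medical update in both arms at 3, 6 and 12 months, though it is not named as an adverse-event instrument. Participants in both arms can also contact an educator or a study physician, and safety is reviewed every two months. No between-arm safety test is planned. The visit count is right, but the consequence is mainly for descriptive safety counts.

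**Conclusion.** The point holds as a gap in outcome collection. Following the plan as written, A1c and distress data that could be obtained remotely may be lost, partly for reasons linked to A1c or to sustained CGM use. This strains the intention-to-treat comparison without contradicting it.

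The expected effect on the A1c estimate is small under the assumptions shown: about 0.006 to 0.051 percentage points for 1 to 3 excess removals. The direction is open, because the removal grounds mix low-glucose, high-glucose and compliance reasons. It is negligible if removals are rare or balanced. The number of withdrawals for non-compliance is unknown; section 1.2.2 cites 27% stopping CGM within a year, but gives no 12-week rate and no rate of investigator withdrawal.

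Unequal scheduled elicitation of adverse events is a minor, secondary matter. The case for acting rests on low cost and on the loss being irreversible, not on a large expected bias.

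**What to change.** 1. In 3.7 and 4.4, leave the clinical criteria as they are, but separate stopping CGM or sessions from stopping follow-up. Unless the participant withdraws consent, keep sending A1c kits and REDCap surveys at 3, 6 and 12 months.
2. In 2.7, state that these values enter the intention-to-treat analysis, and state in advance how A1c measured during pregnancy is handled.
3. Report removals and withdrawals by arm and reason.
4. Secondary: add identical adverse-event questions to the existing 3-, 6- and 12-month demographic/medical update in both arms, base any by-arm event summary on them, and report events raised in ONBOARD sessions separately.

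Cost: a short amendment and a few survey items, since kits and surveys are already remote and planned for everyone enrolled. The downsides are slightly longer surveys and continued contact with people who have stopped CGM.
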